3 ASSESSMENT AND MANAGEMENT OF RISK

A total of 6 venous cannulas will be inserted during the study; 3 on each metabolic test day (one in the elbow for infusion, one in the hand for blood sampling, and one in the elbow for blood sampling). This will involve the insertion of a small needle into the vein to place the cannula. This may cause dizziness and/or nausea if the subject is uncomfortable with needles or blood draws. There is also the possibility of bruising at the needle site. The cannulation will be conducted by trained research nurses and pressure will be applied to the needle site after cannula removal to prevent bruising. Trained first aiders will also be closely available. Per test day, 210 mL blood will be taken over the course of 5.5 hours.

The hyperinsulinaemic-euglycaemic clamp is a procedure routinely used in human physiology research, and [name], [name], and [name] all have significant experience in independently performing this procedure. Co-infusion of an amino acid mixture will be performed to create hyperaminoacidaemic conditions that mimic the postprandial state following food ingestion. This amino acid mixture is a standard product used in clinical care. The main risk of running this procedure is uncontrollable hypoglycaemia. Blood glucose concentrations will be closely monitored every 5 min using a bedside glucose analyser, and the glucose infusion rate will be adjusted accordingly. If blood glucose cannot be maintained, insulin infusion will be stopped immediately, glucose infusion will be further increased, and a carbohydrate-rich drink (present in the room) will be provided to the participant. A minimum of two investigators, of which minimally one of them is emergency first aid-trained, will be in the room at all times. Medical cover will be on call (present in the building) during the insulin infusion.

The acipimox drug may cause some mild-moderate side effects in approximately 2 out-of 10 people. These side effects can include: skin rash; red 'flushed' skin; itching; sensations of hot skin. Less common effects include stomach pain and weakness. The salbutamol drug may cause mild-moderate side effects in approximately 1 out-of 10 people. These side effects can include fine tremor ('shaking', especially of the hands), headache, dizziness, and nausea. Less common side effects can include arrhythmias, low blood pressure, and muscle pain. These reactions usually disappear after 3 days, and failure of symptom reversal in a standard setting normally involves a participant being asked to stop taking the drug. Since participants in the current study are healthy volunteers who will only be taking the drugs for 2 days, no persistent side effects are expected. A clinical doctor ([name]) will be available for advice throughout the study.

Limb immobilization is a model routinely used to study muscle atrophy in humans, and our previous studies (Dirks et al. 2014 *Acta Physiol*, Dirks et al. 2016 *Acta Physiol*, Wall et al. 2013 *J Clin Endocrinol Metab*, Wall et al. 2014 *Acta Physiol*, Wall and Dirks et al. 2016 *AJP Endo Metab*) have used 3-14 days of forearm and leg immobilization in >100 healthy young volunteers without any problems. Forearm immobilization may lead to psychological limitations of having one arm in a cast. During the 2-day immobilization period, participants will likely experience difficulties in performing their daily activities due to only being able to use one arm. A sling will be provided to wear during the day, and a waterproof cover to protect the cast during showering. Any loss of muscle mass and strength that may occur will likely be smaller than 1%, and will restore quickly upon remobilization due to the inclusion of healthy young volunteers.

There will be a time burden on the participant, for which they will receive recompense. The time burden will be spread over a period of around 1.5 weeks, and they will only be required to visit the laboratory for a total of 4 visits. The largest cumulative time burden will be that required to complete the two metabolic test days, approximately 6.5 hours per day.

During the two days of forearm immobilization, participants will be asked to consume a controlled diet and nothing else. Because this diet will be calculated per participant to ensure energy-balanced

conditions, and participants are asked to indicate any food products they cannot or will not eat, the controlled diet should provide adequate dietary intake and not feel as too much of a burden for participants. Of note, this approach has been used in 4 separate studies from the Nutritional Physiology research group, and has proven successful in maintaining energy balance during the studies.

The hyperinsulinaemic-euglycaemic-hyperaminoacidaemic clamp is occasionally associated with gastro-intestinal issues in the last hour of the 3-hour clamp, including vomiting and diarrhoea. To prevent these issues from occurring, we will administer 10 mg metoclopramide hydrochloride intravenously in an already present elbow cannula after 2 hours of the clamp.

Subjects can contact the CI at any time (24/7) if they have concerns or need help. [name] will be available for advice throughout the supplementation period.

4 OBJECTIVES AND OUTCOME MEASURES/ENDPOINTS

4.1 Primary objective

Determine the impact of reduced muscle lipid availability and increased glycolytic flux on forearm glucose uptake during short-term forearm immobilization in healthy volunteers.

Research question: Does lowering muscle lipid availability and increasing glycolytic flux attenuate the immobilization-induced decline in forearm glucose uptake?

Null hypothesis: Lowering muscle lipid availability and increasing glycolytic flux does not attenuate the immobilization-induced decline in forearm glucose uptake.

3.2 Secondary objectives

Determine the impact of reduced muscle lipid availability and increased glycolytic flux on muscle protein synthesis, and forearm nutrient balance during short-term forearm immobilization in healthy volunteers

3.3 Primary outcome

The primary outcome measure of this study is forearm glucose uptake, as a measure of insulin sensitivity, measured using the arteriovenous-venous forearm balance technique. This will be measured under hyperinsulinaemic-euglycaemic conditions, which is the gold standard for assessing insulin sensitivity *in vivo*.

3.4 Secondary outcomes

Secondary outcome measures include postabsorptive and postprandial muscle protein synthesis, forearm branched-chain amino acid and fatty acid balance, and forearm volume.

3.5 Table of endpoints/outcomes

Objectives	Outcome Measures	Timepoint(s) of evaluation of this outcome measure (if applicable)
Primary Objective Determine the impact of reduced muscle lipid availability and increased glycolytic flux on forearm glucose uptake during short-term forearm immobilization in healthy volunteers.	Forearm glucose uptake	During the steady-state phase of the hyperinsulinaemic-euglycaemic clamp, during the metabolic test days prior to and immediately following 2 days forearm immobilization
Secondary Objectives Determine the impact of reduced muscle lipid availability and increased glycolytic flux on muscle protein synthesis, and forearm nutrient balance during short-term forearm immobilization in healthy volunteers	Postabsorptive and postprandial muscle protein synthesis Forearm branched-chain amino acid and fatty acid balance Forearm volume	During the metabolic test days

5 TRIAL SETTING, DESIGN, AND PROCEDURES

This study is a randomized, double-blind, placebo-controlled trial with a parallel group design in healthy young volunteers. This study will determine the impact of pharmacological manipulation of substrate availability on insulin sensitivity, and anabolic sensitivity during 2 days of forearm immobilization. This study comprises of four study visits, depicted in the study schematic on Page 11 and described in detail in paragraph 5.5 below.

This study is a single-centre study, with all visits performed in the Clinical Research Facility at the Royal Devon & Exeter NHS Foundation Trust. Dispensing of the drugs will be performed by the Clinical Trials Pharmacy at the Royal Devon & Exeter hospital in Exeter.

5.1 Recruitment

Participants will be recruited via convenience sampling. Participants will be recruited via posters, flyers, social media, and word of mouth, from the general public of Exeter and the surrounding areas.

5.2 Screening

Participants will be asked to meet the investigator so that the study can be explained to them in detail, and it is clear what they can expect from the research team and what will be expected of them. Assuming they are happy with what has been discussed, they will then provide written consent. Subsequently, they will complete a medical screening questionnaire and have their height, weight, body composition, and blood pressure measured. All in-and exclusion criteria (please see Section 6) will be assessed. The CI will discuss any issues about eligibility to take part with the medical collaborator.

5.3 Payment

The participant will receive an inconvenience allowance of £125, which will be transferred to their bank account of choice by the University of Exeter finance department. Payment for participants who withdraw from the study or are removed from the study will be dealt with on case-by-case basis.

5.4 Consent

After registering interest, the study will be explained in detail to the participant via email, and they will be given the participant information sheet. They will be asked to carefully read the document, so that they can generate any initial questions. This will occur at least one week in advance of screening. Upon meeting the participant face-to-face the study will be verbally explained in detail. This will include explaining to the participant what they can expect were they to participate, including details of all the procedures involved and time commitments. It will also be made clear what is expected of them. Potential participants will be encouraged to ask any questions they may have. It will be explicitly stated that participants can withdraw at any point during the study without giving a reason, and that they can be afforded time to decide on whether they wish to take part. If they are satisfied, and want to participate in the study, they will subsequently sign the informed consent form (all done under the supervision of an investigator who has undergone informed consent training).

Consent will be sought for surplus muscle samples to be used for ancillary studies subject to additional ethical approval, with the participant having the choice of whether to place restrictions on sample use or not (see informed consent form).

5.5 Trial procedures

Please refer to page 11 for trial flow chart and schematic of the metabolic test days. The trial procedures are described below:

Screening visit (visit 1):

- Firstly, participants will be asked to meet the investigator so that the study can be explained to them in detail, and it is clear what they can expect from the research team and what will be expected of them. Assuming they are happy with what has been discussed, they will then provide written consent. Subsequently, they will complete a medical screening questionnaire and have their height, weight, body composition (Bodpod), and blood pressure measured.
- Participant's caloric requirements will be calculated by estimating Resting Metabolic Rate via the Henry equation, and then multiplying this value by an activity factor derived from the International Physical Activity Questionnaire (IPAQ) questionnaire.
- Forearm volume will be measured via anthropometry.
- Participants will be asked for any allergies or intolerances to ensure they can eat everything they will receive as part of the standardized diet.
- Participants will be provided with a food diary to record their habitual dietary intake for 3 consecutive days, including 2 week days and 1 weekend day.

Baseline metabolic test day (visit 2):

- Approximately 1 week prior to casting, at 8 AM, participants will visit the Clinical Research Facility at the Royal Devon & Exeter NHS Foundation Trust in an overnight fasted state for a metabolic test day.
- The following cannulas will be inserted by a trained research nurse: 1) retrogradely into a deep antecubital vein (draining the muscle bed) of the non-immobilised arm, 2) retrogradely into a superficial dorsal hand vein of the to-be-immobilised hand, and 3) anterogradely into an antecubital vein in the elbow of the to-be-immobilised arm for infusion of insulin, glucose, amino acids, and stable isotope amino acids. The cannulated hand will be placed into a hand-warming unit (air temperature 55°C) to arterialize the venous drainage of the hand.
- After insertion of all cannulas, a primed, continuous stable isotope infusion of L-[ring-²H₅]-phenylalanine (prime: 0.5 mg·kg⁻¹, infusion 0.5 mg·kg⁻¹·h⁻¹) will be started with participants in a supine position. Using this tracer approach we will be able to calculate muscle protein synthesis and plasma leucine oxidation.
- At t = 2.5 h, a hyperinsulinaemic-euglycaemic-hyperaminoacidaemic clamp will be started. For this, insulin will be infused at a rate of 50 mU·m⁻²·min⁻¹, and a simultaneous infusion of 20% glucose will be started to maintain euglycaemia at 5.0 mmol·L⁻¹. A 0.3% potassium chloride solution will be infused in the (to be) immobilized arm at a rate of 1 ml/kg body weight/h during the 3-h clamp to maintain plasma potassium concentrations [25]. Hyperaminoacidaemia will be induced by infusion of an amino acid solution (Primene 10%, Baxter) at BCAA concentrations of 700 μmol·L⁻¹. This concentration was chosen as it is the average postprandial BCAA concentration following mixed meal ingestion in the pilot study. Primene will be 7% enriched with L-[ring-²H₅]-phenylalanine to prevent a decrease in plasma enrichments with Primene infusion. Measurements of blood glucose (Yellow Springs Instruments; every 5 min) and BCAA (spectrophotometric assay, [26]; every 20 min) concentrations will be performed at the bedside, and the infusion rate of glucose and amino acids adjusted accordingly to maintain steady state. Throughout the entire 5.5 h infusion period, repeated arterialised-venous (AV) and deep-venous (V) blood samples will be taken in order to calculate forearm AV-V balance of glucose (i.e. insulin sensitivity), amino acids, and free fatty acids using the Fick principle [27]. Prior to every blood sample, brachial artery blood flow will be measured using Doppler ultrasound.

- After 2 hours of the 3h clamp, a single dose of 10 mg metoclopramide hydrochloride will be administered intravenously in an antecubital elbow cannula, to prevent potential gastrointestinal issues during the final hour of the clamp.
- Following the 3 h clamp, infusion of insulin, amino acids and stable isotope amino acids will be stopped while infusion of glucose will be decreased in a stepwise manner based on blood glucose concentrations. The last 30 min of the clamp will be used to calculate the mean glucose infusion rate (GIR) and mean amino acid infusion rate. Participants will be monitored for minimally 20 min following cessation of the glucose infusion before they are allowed to leave the laboratory.

Forearm casting and drug dispensing (visit 3; to take place between 7 and 28 days after visit 2):

- In the morning at 7:30 AM, participants will visit the Clinical Research Facility at the Royal Devon & Exeter NHS Foundation Trust in an overnight fasted state.
- A fiberglass forearm cast (randomized between dominant and non-dominant arm) will be applied from below the elbow to approximately 2-3 cm below the finger tips, to immobilize the wrist. Participants will be given a sling to wear at all times, except for during sleeping and showering. A waterproof cover will be provided to cover the cast during showering.
- Participants will then receive the food products for the controlled diet, which they will consume during the 2 days of forearm immobilization. Participants will be fed in energy balance, with energy requirements calculated as basal metabolic rate (Henry equations) times an activity factor (IPAQ questionnaire). The diet consists of 1.2 g/kg body weight/day protein (approx. 10-15 en%), 50-55 en% carbohydrate, and 35 en% fat. The diet will be composed of three main meals (i.e. breakfast, lunch, dinner) and snacks, and will contain normal food products. A food diary including recipes for the evening meals will be given, and the entire diet will be explained.
- Lastly, participants will visit the Clinical Trials Pharmacy at RD&E to collect their allocated treatment. Instructions on the times and way to ingest the treatment is provided by trained staff, and a treatment log will be provided. The first out of eight doses will be taken.
- Participants will be sent home, and will return to the CRF two days later for visit 4.

Post-immobilization metabolic test day (visit 4):

- In the morning at 8 AM, participants will visit the Clinical Research Facility at the Royal Devon & Exeter NHS Foundation Trust in an overnight fasted state.
- The metabolic test day will be repeated.
- The fiberglass cast will be removed.

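### Section 5.5 places the deep-venous cannula behind the primary outcome in the uncasted arm, against the study's stated aim of measuring immobilised muscle

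*Combined protocol and SAP*

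**What the plan says.** Section 5.5 (visit 2) lists three cannulas:

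- The deep-venous sampling cannula goes "retrogradely into a deep antecubital vein (draining the muscle bed) of the non-immobilised arm".
- The arterialised sampling cannula goes "retrogradely into a superficial dorsal hand vein of the to-be-immobilised hand".
- The infusion cannula goes "anterogradely into an antecubital vein in the elbow of the to-be-immobilised arm for infusion".

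The clamp description in the same section gives the infusion side again for potassium chloride: the "solution will be infused in the (to be) immobilized arm". It then says that arterialised and "deep-venous (V) blood samples will be taken in order to calculate forearm AV-V balance of glucose", using the Fick principle. Brachial artery flow is measured by Doppler before each sample, with no arm named.

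At visit 3 the cast "will be applied from below the elbow to approximately 2-3 cm below the finger tips". For visit 4 the text says "The metabolic test day will be repeated", and the next bullet says "The fiberglass cast will be removed". It mentions no change of arm between visits 2 and 4.

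Elsewhere, section 2 (Rationale) says the study will describe the metabolism of inactive muscle. Section 4.1 asks whether the drugs lessen the fall in forearm glucose uptake caused by immobilisation. Section 9.1 powers the trial on a 13% fall (SD 8%) seen in pilot data after 2 days of forearm immobilisation. Section 3 counts three cannulas per test day but names no arm.

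**The concern.** An arteriovenous balance describes the tissue drained by the sampled vein. With the deep vein cannulated in the uncasted arm, the calculated glucose uptake belongs to a forearm that was never immobilised. The same holds for the amino acid and fatty acid balances, and for any protein synthesis estimate that uses deep-venous samples. Forearm volume, measured by anthropometry, is not affected.

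Two consequences follow if staff do what the text says. First, the disuse-related fall on which the trial is powered would not be observed in the limb where it is expected. Second, both drugs are taken orally, and section 7 describes Acipimox as improving insulin sensitivity. A systemic drug effect in an arm in normal use could therefore be read as protection against disuse, which is a different conclusion from the one section 4.1 seeks.

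**Working it through.** **Step 1: can the text be read another way?** Non-immobilised could in principle mean not yet immobilised, since visit 2 precedes casting. The same bullet rules this out, because it uses to-be-immobilised for the hand and infusion cannulas. The potassium chloride sentence agrees with that layout. All four side labels are mutually consistent, so staff would find no cue that something is wrong.

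**Step 2: compare the sections.**

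| Place | Limb implied for the primary outcome |
|---|---|
| 5.5, visit 2 cannulas | Uncasted arm (stated) |
| 5.5, visit 4 | Same as visit 2 (repeat, no change stated) |
| 2, Rationale | Inactive muscle, so casted arm (explicit) |
| 4.1, Primary objective | Casted arm (by implication; no arm named) |
| 9.1, Sample size | Casted arm (by implication; pilot arm not named) |

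No visible section presents the uncasted arm as an intended control.

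**Step 3: is the layout workable at visit 4?** The cast extends almost to the finger tips on the side where the dorsal hand vein is to be cannulated and warmed. Cast removal is listed after the repeated test day. In that order the hand site lies under the cast. This rests on the order of the bullets alone, because the timing of removal relative to sampling is not stated.

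**Step 4: reproduce the plan's sample size.** Inputs are from 9.1: placebo -13 (SD 8), Acipimox 0 (SD 8), Salbutamol -4.3 (SD 6), alpha 0.05 (two-sided reproduces the plan), power 80%.

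- Acipimox: d = 13/8 = 1.625. The noncentral t solution is 7.05, so 8 per group.
- Salbutamol: difference 13 - 4.3 = 8.7; pooled SD = sqrt((64 + 36)/2) = 7.07; d = 8.7/7.07 = 1.230. The solution is 11.41, so 12 per group.
- Dropout: 12/(1 - 0.20) = 15 per group, and 3 × 15 = 45.

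These match the plan exactly. The arithmetic is sound, provided the 13% fall occurs in the forearm that is sampled.

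**Step 5: sensitivity.** Let f be the share of the planned between-group difference that the uncasted arm would show. The documents give no value, so f is an assumption shown over a range. SDs are held as in 9.1, with 12 per group (22 degrees of freedom), two-sided 5%, and no multiplicity adjustment, as in 9.1. The effect sizes become 1.625f and 1.230f, and the noncentrality parameter is d × sqrt(12/2).

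| f | Difference, Acipimox / Salbutamol (points) | Power, Acipimox | Power, Salbutamol |
|---|---|---|---|
| 1 | 13 / 8.7 | 96.7% | 82.1% |
| 0.75 | 9.75 / 6.5 | 81.4% | 58.0% |
| 0.5 | 6.5 / 4.35 | 47.7% | 30.2% |
| 0.25 | 3.25 / 2.2 | 15.9% | 11.1% |
| 0 | 0 / 0 | 5% | 5% |

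Simulation with 200,000 trials per setting at f = 1, 0.5 and 0 agrees to within 0.1 percentage point. At f = 0.5, 80% power would need 25 (Acipimox) or 43 (Salbutamol) completers per group instead of 12. These counts show scale only: a larger sample would not repair measurement in the wrong limb.

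**The case against.** The strongest reply is that this is a drafting slip. The arm labels look swapped, experienced staff would probably cannulate the intended arm, and the page 11 schematic, to which section 5.5 refers readers, may show the correct layout. If the cast is still on at visit 4, the written layout could not be carried out and the slip would be noticed. If the cast comes off first, the unworkability point disappears.

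Much of this is fair. It limits the certain part of the finding to the conflict in the text and makes the consequence conditional. It does not remove the conflict: section 5.5 is the only visible written instruction for cannulation, and a correct schematic would mean that the protocol contradicts itself on how the primary outcome is obtained.

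A second objection is that only the Rationale conflicts explicitly, because 4.1 and 9.1 refer to the forearm without naming an arm. That is correct, although no other reading of 4.1 and 9.1 is natural.

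A third is that the power range is hypothetical and that a systemic drug effect could produce a group difference in the uncasted arm without any disuse decline. That also stands: f is assumed and need not be small. The main issue is therefore validity, with power as an illustration. A well-powered difference in an active forearm would still not answer the question in 4.1.

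**Conclusion.** The concern holds and must be fixed. As written, the procedure for the primary outcome samples the uncasted forearm at both test days. It contradicts the Rationale explicitly, and the primary objective and the power basis by clear implication. The contradiction is certain on the visible text; measurement in the wrong limb would follow only if staff work to that text. The loss of power cannot be fixed at one figure. It ranges from none at f = 1 to a complete loss (5% for both comparisons) at f = 0, under the assumptions of unchanged SDs and 12 completers per group. The stated sample size of 45 is not in dispute.

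**What to change.** Reconcile the visit 2, 3 and 4 text of section 5.5, and the page 11 schematic, with sections 2, 4.1 and 9.1:

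- For both test days, name the (to-be-)immobilised arm as the site of deep-venous sampling and of the Doppler flow measurement, so that flow and concentration difference refer to the same forearm. The cast starts below the elbow, so it does not cover this site.
- Place the arterialised hand sampling in the opposite arm.
- Restate every infusion site, including potassium chloride, so that nothing is infused into the sampled limb. Moving only the deep-venous cannula would leave the infusions in that limb. Say which elbow cannula is meant where the text is currently unspecific.
- State that the sampled arm is the same at visits 2 and 4.
- Have the sponsor state when the cast is removed relative to sampling.

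The cost is protocol wording only. There are still three cannulas per test day, with the same samples, visits and sample size.
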